### 8.3. Sample Size Justification

The Symptom Response definitions for this study will be derived from the subjects' FLU-PRO questionnaire responses as described in [Section 11.2.1](#). The FLU-PRO-derived endpoint is expected to track very closely to return to usual health status (a daily yes/no question in the FLU-PRO questionnaire), which in turn is expected to track very closely to ability to perform 100% of normal activities. We assume, therefore, that the cumulative distributions of time to Symptom Response for the placebo treatment group will closely reflect historical data from Romark Study RM08-3002 for time from first dose until the EV/RV-infected subjects report that they are able to perform 100% of usual activities (see placebo curve in chart below). Then, to calculate sample size, we assume that treatment with NTZ treatment should result in reduction of at least 48 hours in median time to symptom response. The following curves have been developed for determining sample size.

Based upon these curves, a sample size of 530 subjects with laboratory-confirmed EV/RV infection (i.e. 265 for each of the 2 groups) will provide 90% power to detect a statistically significant difference in the survival distributions between the NTZ and placebo groups (2-sided  $\alpha=0.05$ ). This calculation was performed for the Gehan rank test using SAS PROC POWER (SAS 9.4) with the curves shown above (proportion not recovering by the end of each day was used as input) and censoring at Day 21 (hour 504). Assuming that up to 12% of subjects will have incomplete data, we arrive at a sample size of 600 subjects in total, 300 per treatment group to yield at least approximately 530 with complete data (all EV/RV-infected subjects who receive at least one dose of study medication will be included in the primary analysis with subjects with incomplete data censored as of their last entry).

Based upon these calculations, the study will enroll at least 600 subjects with laboratory-confirmed EV/RV infection up to a maximum of 700 subjects with laboratory-confirmed EV/RV infection.

#### 8.4. Data Collection

Data will be collected using an electronic data capture (EDC) system and electronic subject diaries. Medical history and adverse events will be coded using the latest version of MedDRA. Prior and concomitant medications will be coded using the latest version of WHO Drug.

### 9. DATA DEFINITIONS AND CONVENTIONS

#### 9.1. Analysis Populations

Three populations will be designated for the purpose of these analyses:

**Table 2: Definition of Analysis Populations**

Table Analysis Population	Definition
Intent to Treat (ITT)	All subjects who receive at least one dose of study medication
Intent to Treat Infected (ITI)	The subset of the ITT population who are positive for EV/RV by RT-PCR at any of the Baseline, Day 2 or Day 3 visits
Per Protocol	The subset of the ITI population with no major protocol deviations that may have an effect on the integrity of the data or the evaluation of effectiveness

## 9.2. Data Presentation Conventions

The following conventions are applied to all data presentations and summaries.

**Table 3: Data Presentation Conventions**

Data	Presentation Convention
Descriptive statistics for continuous variables	Include the number of subjects with available data, mean, standard deviation, median, first quartile, third quartile, minimum and maximum values
Descriptive statistics for categorical variables	Include a count of subjects with each response and percentage of subjects with each response out of the total number of subjects per population or treatment group, as applicable
Means and medians for continuous variables	Format to one more decimal place than the measured value
Standard deviations for continuous variables	Format to two more decimal places than the measured value
Minimums and maximums for continuous variables	Format to the same number of decimal places as the measured value
Number and percent for categorical variables	XX (XX.X%)
Date variables	DDMMYY YYYY
Time variables	HH:MM (24-hour clock)
P-values	Present five decimal places
	If less than 0.00001, present as <0.00001
	If rounded result is 1.00000, present as >0.99999
All decimal-containing data, where possible	Presentation should be decimal-aligned

## 9.3. Handling of Unscheduled Assessments

Results of unscheduled assessments will be included in listings, but will not be used in descriptive statistics.

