5.8. Unscheduled Visit

Subjects returning to the clinic for an unscheduled visit due to worsening symptoms or adverse events will be evaluated at the discretion of the Investigator as is medically warranted. Tests and/ or procedures performed at this visit may include, but are not limited to, the following:

1. Brief physical examination (body weight and vital signs with nursing physical assessment) including symptom directed physician physical examination as required by subject symptoms. Vital signs will include blood pressure, pulse, respiratory rate and oral temperature (use standard electronic oral thermometer provided by Sponsor).
2. Collection of two nasopharyngeal swabs using nylon flocked dry swabs (Copan Diagnostics) for RT-PCR and culture.
3. Collection of blood sample for laboratory safety tests.
4. Collection of urine sample for routine urinalysis.
5. Review of compliance with study medication.
6. Review and recording of concomitant medications.
7. Review and recording of adverse events/side effects.

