**Table 4: Handling of Missing Data**

Data	Handling Convention
Adverse event onset date	
If onset date is completely missing, impute with the date of first dose.
 
If year is missing, impute with the year of enrollment.
 
If only year or if year and day are present:
 
 
• If year = year of first dose, then set month and day to the date of the first dose.
 
• If year < year of first dose, then set month and day to December 31.
 
• If year > year of first dose, then set month and day to January 1.
 
 
If month and year are present, but day is missing:
 
 
• If year = year of first dose and 
 
– If month = month of first dose, then set day to day of first dose.
 
– If month < month of first dose, then set day to the last day of the month.
 
– If month > month of first dose, then set day to the first day of the month.
 
 
 
• If year < year of first dose, then set day to the last day of the month.
 
• If year > year of first dose, then set day to the first day of the month.
 
• For all other cases, set onset date to the date of first dose.
 

Adverse event end date	If the end date is partially or completely missing, set to the last date the subject was known to be in the study.
Concomitant medications start date	
If start date is completely missing, it will not be imputed.
 
If only year or if year and day are present, set the month and day to January 1.
 
If year and month are present and day is missing, set day to the first day of the month.

Concomitant medications end date	If end date is completely missing, it will not be imputed. If only year or if year and day are present, set the month and day to December 31. If year and month are present and day is missing, set day to the last day of the month.
Concomitant medications time of dosing	If time of dosing is missing for symptom relief medication, it will be imputed as the time of the FLU-PRO Questionnaire completion for that date.

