### **12.1.3. Laboratory Results and Changes from Baseline**

Numerical hematology and serum biochemistry values will be converted to SI units and classified as Normal, Grade 1, Grade 2, Grade 3 or Grade 4 according to reference ranges indicated in the protocol toxicity grading scale tables (see Protocol Appendix II). Urinalysis results will be classified as Normal or Abnormal based on reference ranges provided by the central laboratory.

Hematology, serum biochemistry, and urinalysis laboratory results and change from Baseline will be summarized using descriptive statistics for each visit.

Shift tables will display shifts from Baseline in laboratory results classification (Grade 1/2/3/4 or Normal/Abnormal) by study day.

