#### 12.1.4. Summaries of Vital Signs Results and Changes from Baseline

Vital signs data will be classified as Normal, Grade 1, Grade 2, Grade 3 or Grade 4 based on the reference ranges indicated in the protocol toxicity grading scale tables (see Protocol Appendix II). If two vital signs values are available in the database for one analysis time point (e.g., Day 7 Visit), the later value will be used for the analysis.

Vital signs results and change from Baseline will be summarized using descriptive statistics for each visit.

Shift tables will display shifts from Baseline in vital signs classification (Grade 1/2/3/4) by study day.

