**Table 16: Data Presented in Safety Listings**

Listing	Data Presented
Adverse Events	MedDRA SOC MedDRA preferred term Reported term Onset date End date Severity Serious (Y/N) Relation to study drug Outcome Change in study drug dosage Treatment required
Hematology Laboratory Results Serum Biochemistry Laboratory Results Urinalysis Laboratory Results	Visit Date of visit Laboratory test Result Result units Lower limit of normal Upper limit of normal Classification (L/N/H)

Listing	Data Presented
Plasma Tizoxanide and Tizoxanide Glucuronide Results	Visit Date of visit Tizoxanide concentration (µg/mL) Tizoxanide glucuronide concentration (µg/mL)
Vital Signs Data	Visit Date of visit Weight (kg) Systolic blood pressure (mmHg) Diastolic blood pressure (mmHg) Pulse (bpm) Respiratory rate (bpm) Oral temperature (°F)
Physical Examination Data	Visit Date of visit Body system Result (Normal/Abnormal/Not Done) Abnormality

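### Unscheduled laboratory and vital-sign results are kept out of every summary and shift table, and no worst post-baseline grade table is planned; separately, the missing-year rule can date an adverse event before the first dose

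*SAP*

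**What the plan says.** - SAP 9.3: "Results of unscheduled assessments will be included in listings, but will not be used in descriptive statistics".
- SAP Table 3, on descriptive statistics for categorical variables: "Include a count of subjects with each response and percentage of subjects with each response". On this reading section 9.3 covers grade counts and shift tables as well as means.
- Protocol 5.8 describes who attends such a visit: "Subjects returning to the clinic for an unscheduled visit due to worsening symptoms or adverse events". Vital signs, safety bloods and urinalysis may all be done there.
- Protocol 5.2, 5.6 and 5.7 schedule safety bloods and urinalysis at Baseline and Day 7 only. Vital signs are taken at screening, Day 7 and Day 22.
- SAP 12.1.3: "Shift tables will display shifts from Baseline in laboratory results classification (Grade 1/2/3/4 or Normal/Abnormal) by study day". The list of displays in SAP Appendix 2 contains no table of worst post-baseline grade.
- SAP 12.1.4, where two vital-sign values exist for one time point: "the later value will be used for the analysis".
- SAP Table 16: the laboratory listings give visit, date, result, units, limits of normal and a low/normal/high flag, but not the toxicity grade. The vital-signs listing has no classification.
- SAP Table 4, on adverse event onset: "If onset date is completely missing, impute with the date of first dose"; but "If year is missing, impute with the year of enrollment".

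**The concern.** Values taken because a subject felt worse are the ones most likely to be abnormal, and they are the ones left out. With one scheduled post-baseline blood sample, on Day 7, an abnormality that comes and goes during the five days of treatment can be tabulated as normal at both ends. Protocol 8.4.3 makes the safety analysis purely descriptive, so no other analysis of these measurements would pick them up.

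The missing-year rule is a smaller matter of logic. The study was planned to run from August 2018 to April 2019, so follow-up crosses New Year for some subjects. For them the enrollment year can be the wrong year.

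**Working it through.** The plan gives no figure on this point. The check is to trace the rules; the arithmetic only sets a scale.

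**Unscheduled values.** Take a hypothetical subject with normal ALT at Baseline, a Grade 3 value at an unscheduled visit on Day 4, and a normal value on Day 7.

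1. Summaries and shift table (SAP 12.1.3): Day 4 is removed by 9.3, so the subject is shown as normal to normal.
2. Other graded laboratory tables: none. Displays 14.3.2.1 to 14.3.3.2 are by-visit summaries and shift tables.
3. Adverse event tables (SAP 12.1.1, 12.1.2): the value enters only if the investigator reports it. Protocol section 10 requires a laboratory change to be clinically significant.
4. Listing (SAP Table 16): the result, its limits and a high flag appear, without a grade.

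So the value reaches a graded table only by being reported as an adverse event. Vital signs follow the same path through display 14.3.5.2.

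Protocol 5.9 adds an open point. A subject who discontinues early has Day 7 or Day 22 procedures at that time, and the SAP does not say whether these count as scheduled.

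*Scale.* The documents give no rate of unscheduled visits. Planned total enrollment is 700 / 0.40 = 1,750, which agrees with protocol 8.1. If 2% to 5% of subjects had an unscheduled visit with bloods (an assumption), that is 0.02 × 1,750 = 35 to 0.05 × 1,750 = 87.5, about 88. These would be subjects with some excluded value, not subjects with a Grade 3-4 value.

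**Two vital signs at one time point.** Abnormal then normal is tabulated as normal; normal then abnormal is tabulated as abnormal. The rule is neutral in direction, but it does not give the worst value.

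**Missing year.** Take a first dose on 20 December 2018 and an event in January 2019 whose year was not recorded. Table 4 gives:

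| Known parts | Imputed onset | Days from first dose |
|---|---|---|
| Day and month (5 January) | 5 January 2018 | -349 |
| Month only (January) | 31 January 2018 | -323 |
| Day only | 20 December 2018 | 0 |
| Nothing | 20 December 2018 | 0 |

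Protocol section 10 counts only events after the first dose as adverse events, so the first two dates are impossible.

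*Scale*, assuming even accrual. With F days of follow-up after the first dose (21, or 24 with the Day 22 visit window) and N accrual days, the share of subjects whose follow-up crosses New Year is F / N.

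- Lowest: 1 August to 30 April, N = 273, F = 21. 21 / 273 = 7.7%, about 135 of 1,750.
- Highest: 1 September to 31 March, N = 212, F = 24. 24 / 212 = 11.3%, about 198 of 1,750.

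The share of all follow-up days that falls in the later year is about half of this, F / (2N): 3.85% to 5.66%. If 0.5% to 5% of adverse event records lacked only the year (an assumption), and events were spread evenly over follow-up, the number misdated per 1,000 events runs from 1,000 × 0.0385 × 0.005 = 0.2 to 1,000 × 0.0566 × 0.05 = 2.8.

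**The case against.** Most of the information is retained, and several stronger readings fail.

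- *A reader might infer that the grade of an unscheduled value is lost.* It is not. The listing gives result, units and limits, and for most analytes the grade can be worked out from protocol Appendix II. The exceptions are chloride, HDL, LDL and hematocrit, which the appendix grades by clinical consequence. Section 9.3 also does not stop these values from being graded; it stops them from being tabulated.
- *A reader might infer that a Grade 3-4 value has no way into the tables.* It has one. Clinically significant laboratory changes are adverse events (protocol section 10), graded with Appendix II (10.1) and recorded at unscheduled visits (5.8). The SAP counts them by maximum grade and tabulates Grade 3 and above separately. This stands, and it narrows the loss to values not so reported.
- *A reader might infer that the later-value rule hides abnormal readings.* It can do so, but it equally keeps a worse second reading. No systematic under-reporting is shown.
- *A reader might infer that misdated events drop out of the TEAE tables.* The SAP gives no date rule for a TEAE, so this does not follow. The rule that sends all other cases to the first dose might also be read as covering these records, although it sits under the missing-day case.
- *A reader might take 8% to 11% of subjects as affected by the missing-year rule.* That is the share whose follow-up crosses New Year. An error also needs an event in January with a known month and no year. Daily diary entry and real-time edit checks (protocol 5.10, 7.1) make that uncommon.
- *A reader might infer bias between the arms.* That would need different rates of unscheduled visits by arm, on which the documents say nothing.

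It is also fair to say that by-visit means should rest on scheduled values. That supports section 9.3 for those summaries, but not for a question about worst grade.

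**Conclusion.** The point holds in a limited form. Unscheduled laboratory values and vital signs are excluded from all summary and shift tables, and nothing planned replaces them. A transient Grade 3-4 value not reported as an adverse event is absent from every graded table, though still in the listings. This rests on reading shift tables as descriptive statistics, which SAP Table 3 supports.

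The missing-year rule can produce an onset date 323 to 349 days before the first dose in the worked example. Few records would be affected. Such an event may be lost from the TEAE tables if TEAE is defined by onset date, which the SAP does not state.

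The number of subjects affected by either rule cannot be derived from the documents; the ranges above depend on assumed rates and even accrual.

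**What to change.** 1. Keep the by-visit summaries on scheduled values.
2. Add shift tables from Baseline to the worst post-baseline grade for laboratory tests and vital signs, using all post-dose values: unscheduled, repeat and early-termination. For urinalysis, which the SAP classifies as normal or abnormal, use any abnormal post-dose result. Where two vital-sign values exist, take the more abnormal one in this table.
3. Show the grade in the laboratory and vital-sign listings.
4. In SAP Table 4, when the year is missing, choose the year that places the known month and day on or after the first dose and within follow-up; otherwise use the date of first dose. If only the month is known, choose the year in the same way and then apply the existing rule for the day.
5. State how a TEAE is defined, so that the effect of any imputed date is clear.

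The cost is SAP wording and a few extra tables from data already collected. The counts of graded abnormalities may look slightly less favourable.

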#### 9.4. Handling of Missing Data

Missing data will be handled as follows:

**Table 4: Handling of Missing Data**

Data	Handling Convention
Adverse event onset date	
If onset date is completely missing, impute with the date of first dose.
 
If year is missing, impute with the year of enrollment.
 
If only year or if year and day are present:
 
 
• If year = year of first dose, then set month and day to the date of the first dose.
 
• If year < year of first dose, then set month and day to December 31.
 
• If year > year of first dose, then set month and day to January 1.
 
 
If month and year are present, but day is missing:
 
 
• If year = year of first dose and 
 
– If month = month of first dose, then set day to day of first dose.
 
– If month < month of first dose, then set day to the last day of the month.
 
– If month > month of first dose, then set day to the first day of the month.
 
 
 
• If year < year of first dose, then set day to the last day of the month.
 
• If year > year of first dose, then set day to the first day of the month.
 
• For all other cases, set onset date to the date of first dose.
 

Adverse event end date	If the end date is partially or completely missing, set to the last date the subject was known to be in the study.
Concomitant medications start date	
If start date is completely missing, it will not be imputed.
 
If only year or if year and day are present, set the month and day to January 1.
 
If year and month are present and day is missing, set day to the first day of the month.

Concomitant medications end date	If end date is completely missing, it will not be imputed. If only year or if year and day are present, set the month and day to December 31. If year and month are present and day is missing, set day to the last day of the month.
Concomitant medications time of dosing	If time of dosing is missing for symptom relief medication, it will be imputed as the time of the FLU-PRO Questionnaire completion for that date.

## 10. GENERAL CHARACTERISTICS

### 10.1. General Characteristics Tables and Figures

All tables will present data for the overall study and by treatment group.

#### 10.1.1. Disposition of Subjects

The disposition tables will summarize the count and percentage of subjects who completed or discontinued from the study and the mean (SD), median (IQR), and minimum and maximum number of days in the study.

Analysis Population(s): ITT, ITTI

Derived Variables: Number of days in study = date of study completion/early termination – date of randomization + 1

#### 10.1.2. Protocol Deviations

The deviations tables will summarize the count and percentage of subjects with protocol deviations by deviation classification (major or minor) and the common deviation term.

Analysis Population(s): ITT, ITTI

Derived Variables: None

#### 10.1.3. Demographics

The demographics tables will summarize sex, age at screening (years), race, height (cm), weight (kg), BMI (kg/m^2), and smoking status as collected at screening/Baseline using descriptive statistics.

Analysis Population(s): ITT, ITTI

Derived Variables: Age in years at screening = date of screening – date of birth

BMI = weight in kg / (height in cm / 100)

#### 10.1.4. Disease Characteristics

The disease characteristics tables will summarize time since onset of symptoms and baseline virus infection(s) using descriptive statistics.

Analysis Population(s): ITT, ITTI

Derived Variables: None

#### 10.1.5. Prior and Concomitant Medication

The prior and concomitant medication tables will summarize the number and percentage of subjects receiving each medication by Level 4 Anatomical Therapeutic Chemical (ATC) classification and standardized medical name.

Analysis Population(s): ITT, ITTI

Derived Variables: Prior medication classification = medications with stop dates prior to screening date

Concomitant medication classification = medications with administration occurring on or after the date of the first administration of study drug until the end of the study

#### 10.1.6. Medical History and Concomitant Diseases

The medical history and concomitant diseases tables will summarize the number and percentage of subjects reporting each medical history event by MedDRA preferred term and system organ class.

Analysis Population(s): ITT, ITTI

Derived Variables: Medical history classification = events with stop dates prior to screening date

Concomitant disease classification = events with stop dates on or after the date of the first administration of study drug until the end of the study

#### 10.1.7. Treatment Exposure

The treatment exposure tables will summarize the total number of days on therapy and number of tablets taken using descriptive statistics.

Analysis Population(s): ITT, ITTI

Derived Variables: Number of tablets taken = number of doses reported to have been taken in the case report form (CRF) \* 2

### 10.2. General Characteristics Listings

General characteristics listings will include data specified in [Table 5](#) for all subjects presented by subject number and treatment group.

